Radiographic response (brain and spine) will be assessed by MRI with and without contrast (ie, gadolinium). Brain MRI assessments will be conducted during screening (within 21 days prior to first dose of study treatment) and then on Day 1 of Cycles 3, 5, 7, 10, 13, 16, 19, 22 (or within 7 days prior to dosing), after completion of Cycle 24 (or within 7 days prior) and as clinically indicated. **Note:** For DIPG subjects only, post-baseline brain MRI assessments will be performed on Day 1 of Cycles 4, 7, 10, 13, 16, 19, 22 (or within 7 days prior to dosing), after completion of Cycle 24 (or within 7 days prior) and as clinically indicated.

Spine MRI will be also performed during screening (within 21 days prior to first dose of study treatment) for all subjects. If no spinal or leptomeningeal disease is present at screening, subsequent spine MRIs will be obtained on Day 1 of Cycles 7, 13, 19 (or within 7 days prior to dosing) after completion of Cycle 24 (or within 7 days prior) and as clinically indicated. If there is spinal or leptomeningeal disease present at screening/baseline, spine MRIs will be obtained at the same time points as the brain MRI as specified above.

A response assessment should also be performed at EOT visit if the subject has discontinued for reasons other than progression of disease and it has been more than 8 weeks since their most recent scan/response assessment.

[figure not shown]
Response evaluations will be performed locally and by independent central reviewer according to criteria detailed in Section 6.4.1.

Subjects who discontinue treatment will enter a Follow-up Period which will continue every 3 months (\pm 14 days) for up to 5 years from enrollment of the last subject, unless consent/assent is withdrawn, the subject is lost to follow-up or dies. Subjects will be followed by phone or clinic visits for emergence of second primary malignancies (SPMs) (regardless of causal relationship), drug-related SAEs, survival status, and start of any new anticancer therapies. Additionally, subjects who discontinue treatment prior to progression will be followed with MRI tumor response disease assessments every 6 months from treatment discontinuation for the first year off treatment, then annually thereafter, until disease progression or until another anticancer therapy is started, whichever comes first.

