6.2. Treatment Period

The subject will begin treatment upon re-confirmation of eligibility (ie, safety assessments) and subsequent enrollment. The subject must start treatment within 28 days of signing the ICF/IAF. For all subsequent visits, an administrative window of ± 3 days is permitted unless noted otherwise for a particular assessment. Brain and spine MRI assessments can be conducted within 7 days prior to the scheduled timepoint (ie, during study drug rest period). Study visit windows should take into account the subject's investigational product (IP) supply and administration.

Note: Safety laboratory (hematology, serum blood chemistry) and physical examinations do not need to be repeated on Cycle 1, Day 1 if performed within 7 days of starting treatment unless clinically indicated; however, for FCCBP/FCBP subjects, a urine or serum pregnancy test must be performed to assess subject eligibility 10 to 14 days prior to and again within 24 hours prior to the first administration of pomalidomide. The pregnancy test 10 to 14 days prior to initiation of pomalidomide however may be omitted, at the discretion of the investigator, for any FCCBP/FCBP who has high acuity disease requiring immediate treatment with pomalidomide. The pregnancy test within 24 hours prior to the first dose of pomalidomide is required to be performed (refer to Section 6.4.2.9).

The Treatment Period is defined as the time starting from first study drug administration (Cycle 1, Day 1) until permanent study treatment discontinuation. Subjects will be administered pomalidomide on Days 1 to 21 of each 28-day treatment cycle for a maximum of 24 cycles. Pomalidomide will not be administered on Days 22 through 28 of the 28-day treatment cycle.

The following evaluations will be performed at the frequency specified in the Table of Events (Table 4) and further detailed in the protocol referenced Section 6.4. The evaluations should be performed prior to dosing on the visit day, unless otherwise specified.

- Reconfirm eligibility (Cycle 1, Day 1 only)

- IRT registration (Day 1 of each treatment cycle)
- Enrollment via IRT: Day 1, Cycle 1 only
- Concomitant medications and procedures
- Adverse event evaluation
- Assessment of SPM
- Physical examination (including vital signs)
- Height
- Body weight
- BSA calculation
- Lansky/Karnofsky performance status. Karnofsky will be utilized for subjects age ≥ 16 years and Lansky will be utilized for subjects age < 16 years.
- Hematology

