6.4.1.8. Independent Central Response Review

Response evaluations will be based on MRI results obtained at each site and will be assessed locally and by an independent central reviewer. Corticosteroid use and clinical assessments (ie, neurologic status) will also be considered when determining overall response. The local Investigator’s assessment will be used for subject eligibility and treatment decisions. Efficacy based endpoints incorporating tumor assessments (primary and secondary) will be based on the independent central assessment.

Imaging/response data will be centrally collected and checked for quality by an imaging contract research organization (CRO) designated by Celgene. Independent central review (screening/

baseline and post-baseline assessments) will be performed for all MRIs collected for response assessment. Further details regarding MRI acquisition requirements and image submission procedures are outlined in the Imaging Manual.

Details of the central review process and requirements for central imaging review will be described in the independent review charter. Results of the central review will not be provided to the sites.

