7.2.1. Criteria for Starting Subsequent Treatment Cycles

Prior to the start (within 48 hours) of each treatment Cycle (Day 1) the following parameters **MUST** be met:

- ANC \geq 1,000/mm³
- Platelet count \geq 100,000/mm³ (transfusion independent, defined as no platelet transfusion within 7 days and recovery from nadir)
- Does not meet PD or treatment interruption/discontinuation criteria

In addition, subjects **MUST** meet the following within 24 hours prior to the start of each treatment cycle:

- Confirmation of negative serum or urine pregnancy test (sensitivity of at least 25 mIU/mL) in FCCBP/FCBP.
- Confirmation of the use of 2 forms of effective birth control for FCCBP/FCBP and sexually mature males or confirmation of commitment to complete abstinence.
- Completion and documentation of required pomalidomide education and counseling.

If a subject does not meet the above parameters by Day 28 of a treatment cycle, then the subsequent cycle should not be started until these parameters are met. Refer to Section 7.2.2 for dose interruptions/reductions or next cycle delays due to count recovery or non-hematological toxicities.

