4.4. Overall Study Design and Plan

[figure not shown]
Each tumor type/disease indication incorporates the Simon's Optimal Two-stage study design incorporating the following parameters: significance level of 5%, 90% power and a lower and upper boundary of interest of 10% and 40%, respectively, of the primary endpoint. Based on these boundaries, each tumor type/disease indication will enroll up to 20 subjects eligible for the primary endpoint; 9 in stage one and 11 in stage two. Subjects not eligible for the primary endpoint, ie, not contained within the Response Population, If the number of subjects observed with either an OR or long-term SD according to central response review is ≥ 2 , then enrollment shall continue into stage two; otherwise enrollment will close to that specific tumor type/disease

indication. At the end of stage two, if ≥ 5 out of 20, ie, the target ORSDR $\geq 25\%$, of the subjects enrolled across stage one and stage two combined are observed as having an OR or long-term SD then the treatment will be declared positive in that given tumor type/disease indication; otherwise the treatment will be considered negative in that given tumor type/disease indication (

Figure 2).

If, in a given tumor type/disease indication, by the time the eighteenth subject becomes evaluable for the primary endpoint and only two subjects have been observed across stage 1 and stage 2 combined as having either a OR or long-term SD then enrollment to that tumor type/disease indication will be stopped due to a lack of efficacy.

Figure 1: Overall Study Design

[figure not shown]

ICF=informed consent form, IAF=informed assent form, MRI=magnetic resonance imaging, OS=overall survival, PD=disease progression, PFS=progression-free survival, SAE=serious adverse event, SPM=second primary malignancy.

*From last subject enrolled

**Subjects without a PD at time of treatment discontinuation will continue to be followed for MRI tumor assessment (every 6 months for the first year from treatment discontinuation, then annually thereafter).

Figure 2: Simon’s Optimal Two-stage Parallel Phase 2 Study Design

DIPG=diffuse intrinsic pontine glioma, OR=objective response, PD=progressive disease, LTSD= Long-term stable disease.

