6.1. Analysis of Primary Efficacy Endpoint

6.1.1. Objective Response and Long-term Stable Disease Rate

The ORSDR is defined as the percentage of subjects that achieve either a CR, PR or SD maintained for ≥ 6 cycles (≥ 3 cycles for the DIPG tumor type/disease indication) as their best response, divided by the total number of subjects available for the analysis within the given population, eg, subjects contained within the Response Population (primary analysis), the ITT Population, and the Safety Population as outlined within Section 5 of this SAP. The ITT Population will not be used should all enrolled subjects have received at least one dose of study drug. Non-responder subjects are considered subjects with a PD as best response, subjects not having a postbaseline assessment or subjects having not evaluable recorded on their postbaseline assessment(s). The corresponding 2-sided, 95% Clopper-Pearson confidence interval (CI) will also be provided.

Calculation of SD duration starts at the time of first dose of pomalidomide and continues until the date of the first observation of PD is recorded or death due to any cause, regardless of whether the subject achieves a CR and/or PR within that period, or until the date of the last disease assessment if no PD or death is recorded; if the difference is ≥ 6 cycles (≥ 3 cycles for the DIPG tumor type/disease indication), ie, the subject has not had a documented PD before Cycle 7, Day 1 (Cycle 4, Day 1 for the DIPG tumor type/disease indication) and has completed 6 cycles of pomalidomide (3 cycles for the DIPG tumor type/disease indication), then the SD will be considered as being maintained for ≥ 6 cycles (≥ 3 cycles for the DIPG tumor type/disease indication).

For identification of PD for this SD duration calculation, PD is classified as a PD as observed during a response assessment (both during the Treatment Period and the Follow-up Period if applicable); the first time this occurrence is observed is selected as the PD date.

Disease assessments recorded on or after start of a new anticancer therapy will not be considered, nor will disease assessments reported after a PD has been observed.

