6.5. Interim Analysis

Each tumor type/disease indication incorporates the Simon's Optimal Two-stage study design, using a 5% significance level, 90% power, and a lower and upper boundary of 10% and 40%, respectively, for the primary endpoint. For stage one to be evaluated in a given tumor type/disease indication, there must be 9 subjects eligible for the primary endpoint analysis. Subjects If at least 2 subjects are observed as having as either a CR, PR or long-term SD according to central response review, ie, at least 2/9 ($\geq 22\%$), then enrollment in to stage two will continue as planned; otherwise that tumor type/disease indication will be closed to enrollment and the treatment in that tumor type/disease indication considered inefficacious.

If, in a given tumor type/disease indication, none of the first 8 subjects evaluable for the primary endpoint have an OR or long-term SD before the ninth subjects is enrolled, that particular tumor type/disease indication will close to enrollment due to early identification of futility. Similar, if at the time of the interim analysis the required number of subjects observed with an OR or long-term SD is 5 or more, then the enrollment to that given tumor type/disease indication may to stopped due to the required efficacy across stage 1 and stage 2 to declare the study positive in that tumor type/disease indication having been demonstrated early. Each tumor type/disease

indication is run in parallel to each other meaning the interim analysis per tumor type/disease indication may be conducted at different times, as and when the data becomes available for analysis.

CELGENE PROPRIETARY INFORMATION

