^c Safety laboratory (hematology and serum blood chemistry) and physical examinations do not need to be repeated on Cycle 1, Day 1 if performed within 7 days of starting treatment, unless clinically indicated. FCBP/FCCBP must have pregnancy test performed within 24 hours prior to the initial dosing of pomalidomide.

^d Can also be conducted verbally via phone from the site. Subjects must also be counseled against sharing pomalidomide and donating blood, semen or sperm during therapy until the 28-day post-treatment Safety Follow-up Visit. Pregnancy counseling and potential risks must be conducted on Day 1 of each cycle prior to pomalidomide dispensing or at a minimum of every 28 days during the Treatment Period.

- ^e Subjects who experience toxicity should have appropriate laboratory testing at least twice weekly (3 to 4 days apart or more frequently) until the toxicity has resolved.
- ^f Testing with a sensitivity of at least 25 mIU/mL will be performed in FCBP/FCCBP subjects; refer to Section 6.4.2.9 of the protocol for details. The subject may not receive pomalidomide until the Investigator has verified that the result of the pregnancy test performed on Day 1 (within 24 hours prior to treatment) of every cycle is negative.
- ^g Obtain 10 to 14 days prior to first dose of study drug and again within 24 hours prior to first dose of study drug. **NOTE:** The pregnancy test 10 to 14 days prior to initiation of pomalidomide may be omitted, at the discretion of the investigator, for any FCCBP/FCBP who has high acuity disease requiring immediate treatment with pomalidomide. The pregnancy test within 24 hours prior to the first dose of pomalidomide is required to be performed.
- ^h Screening/baseline MRI can be obtained up to 21 days prior to Cycle 1 Day 1.
- ⁱ Brain/Spine MRIs can be performed within 7 days prior to scheduled timepoint.
- ^j Response/MRI assessment will be performed at the End of Treatment Visit only if the subject has discontinued for reasons other than PD and has been more than 8 weeks since their most recent scan/response assessment.
- ^k Subjects that discontinue treatment prior to disease progression will be followed with MRI tumor assessments every 6 months from treatment discontinuation for the first year off treatment, then annually thereafter until PD, start of a new anticancer therapy, consent/assent is withdrawn, is lost to follow-up, or death.

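### In the high-grade glioma, medulloblastoma and ependymoma strata, long-term SD can depend on the calendar day of the scan scheduled for Cycle 7 Day 1, because the SAP does not map scans in the permitted window to their visit

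*SAP*

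**What the plan says.** SAP 6.1.1 measures SD duration from first dose to first PD or death, or to the last disease assessment if neither occurs. It requires at least 6 cycles (3 for DIPG). It then explains this as meaning that "the subject has not had a documented PD before Cycle 7, Day 1" and that 6 cycles of drug are completed. SAP 6.2.2 repeats the rule.

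Protocol 3.1 schedules brain MRI in the three non-DIPG strata at screening, "then on Day 1 of Cycles 3, 5, 7, 10, 13, 16, 19, 22 (or within 7 days prior to dosing"). Protocol 6.2 says "Brain and spine MRI assessments can be conducted within 7 days prior to the scheduled timepoint" and places this in the drug rest period. The SAP's Table of Events has the same window: "Brain/Spine MRIs can be performed within 7 days prior to scheduled timepoint".

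SAP Appendix A2 (Handling of Dates) gives, as an example of an outcome date, progression dated from the scan that showed it. A2 (Calculations of Cycles) defines Day 1 of a cycle as a study-drug day recorded on the eCRF. No text assigns a scan inside the window to its scheduled visit.

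The endpoint uses central review, and "Results of the central review will not be provided to the sites" (Protocol 6.4.1.8). One condition for starting a cycle is "Does not meet PD or treatment interruption/discontinuation criteria" (Protocol 7.2.1).

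**The concern.** The 7-day window exists for scheduling convenience, but the success rule compares a scan date with a single calendar day. Two subjects with the same history, the same planned dosing and the same central reading at the same scheduled assessment can therefore be classified differently. Each stratum is decided on small counts (at least 2 of 9 to continue, at least 5 of 20 to call the drug effective), so one reclassified subject can change a decision. Where the rule has no defined answer, someone must choose a convention at programming, possibly with outcomes in view.

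**Working it through.** **Design check.** With n1 = 9 and n = 20, let S(p) = P(at least 2 of 9) and R(p) = P(Stage 1 passed and total at least 5 of 20), from exact binomials without the SAP's extra stopping rules. R(0.10) = 0.0349 and R(0.40) = 0.9018, so the stated 5% and 90% are reproduced.

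**Dates, no cycle delays.** Cycle 7 Day 1 is study day 169, which is 6 × 28 = 168 days after first dose.

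*Case A: PD by central review, Cycle 7 dosed.* The subject has SD at Cycle 3 and/or Cycle 5, no CR or PR, and 6 completed cycles. The site saw no PD.
- Scan on Cycle 7 Day 1: 168 days, and not before that day. Success.
- Same assessment 1 to 7 days earlier: 167 to 161 days, and before that day. Failure.

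The rule that PD as best response is a non-response does not apply, because SD was already recorded.

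*Case B: the site also sees PD.* Cycle 7 is not dosed, so Cycle 7 Day 1 has no date under A2. The last Cycle 6 dose falls on day 5 × 28 + 21 = 161. The end of Cycle 6 could then be:
- day 161 + 7 = 168 (SAP 9.1, an exposure rule);
- day 161 + 28 = 189 (A2, last dose plus 28);
- day 169 + 28 = 197 (A2, if discontinuation is recorded on day 169).

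SAP 6.1.1 cites none of these, so the PD condition and the completed-cycles condition are both open.

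*Case C: no PD.* The last scan is 1 to 7 days before Cycle 7 Day 1, with no later assessment. Duration is 161 to 167 days. This fails the numeric test of 168 days but passes the explanatory clause.

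A delay also separates the two tests. If Cycle 7 Day 1 slips 7 days, PD on a scan 1 to 7 days before it falls at 174 to 168 days, which meets the numeric test but fails the clause.

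*DIPG.* The first scheduled post-baseline scan is Cycle 4 Day 1. PD there is the best response and already a non-response for the primary endpoint, unless an unscheduled scan showed SD earlier.

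**Size, PD direction only (assumed inputs).** Let L be the share of subjects with first PD at this assessment after 6 cycles (5% to 10%). Let q be the share of those scans dated Cycle 7 Day 1: 1/8 if spread evenly over the 8 permitted days, or 1/2. Then e = L × q. If the SAP rule gives success rate p, a scheduled-assessment rule gives p − e. On PD cases the successes are nested, so P(decisions differ) is S(p) − S(p − e) at Stage 1 and R(p) − R(p − e) at the end.

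| L, q | e | Stage 1, p = 10% / 25% / 40% | Final, p = 10% / 25% / 40% |
|---|---|---|---|
| 5%, 1/8 | 0.00625 | 2.1% / 1.5% / 0.5% | 0.8% / 2.4% / 0.8% |
| 10%, 1/8 | 0.0125 | 4.2% / 3.1% / 1.1% | 1.4% / 4.9% / 1.7% |
| 5%, 1/2 | 0.025 | 8.3% / 6.4% / 2.3% | 2.4% / 9.8% / 3.7% |
| 10%, 1/2 | 0.05 | 15.4% / 13.6% / 5.1% | 3.3% / 19.7% / 8.5% |

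The chance of at least one such subject, 1 − (1 − e)^n, runs from 5.5% to 37% for n = 9 and from 12% to 64% for n = 20.

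L counts all PD at this assessment, whereas Case A needs Cycle 7 to have been dosed. If that held for half of them, L = 10% with q = 1/2 gives e = 0.10 × 0.5 × 0.5 = 0.025, and the final figure at p = 25% falls from 19.7% to 9.8%.

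**The case against.** **The wording follows the protocol.** Protocol 6.4.1.7 and Appendix C judge long-term SD by status at the end of Cycle 6, and A2 ends a cycle the day before the next begins. When Cycle 7 is dosed, PD dated Cycle 7 Day 1 lies after Cycle 6. This stands: the SAP does not contradict the protocol. But the protocol does not say how a scan on Cycle 7 Day 1 counts, when that scan is also the one that assesses Cycle 6.

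**Other dating rules might apply.** SAP section 6 dates an assessment collected over several days by its last measurement, and the scan-date convention in A2 is only an example. Overall response also uses neurologic status, which is assessed on Day 1. But any single criterion suffices for PD, so a scan alone can fix the date. Where the last-day rule did apply, the result would still turn on dating.

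**The inputs are unsupported.** This stands. The window is placed in the rest period and PD must be ruled out before a cycle starts, which favours scanning before Day 1. So 1/8 is not a floor, and q could be near 0.

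**Stronger readings that the documents do not support.**
- A reader might infer that every discrepancy favours the drug. Case C runs the other way on the numeric test.
- A reader might infer that type I error is inflated. SAP 4.4 sets "a lower and upper boundary of interest of 10% and 40%, respectively, of the primary endpoint", and SAP 6.5 likewise "a lower and upper boundary of 10% and 40%, respectively, for the primary endpoint". That is the endpoint SAP 6.1.1 defines, so 3.5% and 90.2% hold for it.
- A reader might infer that all PD on a Cycle 7 Day 1 scan counts as success. That result is definite only when Cycle 7 was dosed.

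**Conclusion.** The point holds for high-grade glioma, medulloblastoma and ependymoma. With Cycle 7 dosed and PD by central review, scan day alone decides between success and failure. With Cycle 7 not dosed, the rule gives no answer. For a last non-PD scan inside the window, its two halves disagree.

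The size cannot be established from the documents. The tabulated 0.5% to 15% (Stage 1) and 0.8% to 20% (final) measure disagreement with a scheduled-assessment rule, not error rates. They cover the PD direction only, treat all PD at this assessment as affected, and shrink roughly in proportion to the share with Cycle 7 dosed and the share scanned on Day 1. The wording should be settled before outcomes are reviewed, because decisions rest on one or two subjects and the remedy is cheap.

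**What to change.** In SAP 6.1.1 and 6.2.2, classify by scheduled assessment instead of calendar date:

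- PD by central review at the assessment scheduled for Cycle 7 Day 1 (including its 7-day window and a late scan for that visit), or any earlier PD or death, is not long-term SD, whether or not Cycle 7 was started.
- A non-PD result at that assessment with 6 completed cycles is long-term SD.
- If that assessment is missing or not evaluable, a later non-PD central assessment before any new anticancer therapy qualifies. First PD at the next evaluable assessment does not.
- A prior CR or PR remains a success for the primary endpoint.
- State how completion of 6 cycles is derived when Cycle 7 is not dosed.
- Use the same wording for Cycle 4 Day 1 and 3 cycles in DIPG, for consistency. It will rarely change the primary endpoint there.

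The cost is a few sentences and one derivation. No data are added, and the 9 + 11 design and its thresholds stay. The observed rate may change slightly, usually downward. If the 40% was chosen with the present wording in mind, power R(0.40 − e) under the assumptions above would be 88% to 89% (q = 1/8) or 82% to 86% (q = 1/2), against 90.2%.
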